#### *Data collection*

##### *Quantitative data*

Participants will first complete the “American Indian Elder Health Questionnaire” (AIEHQ), based on four surveys administered among AIEs across the country, thus providing a comparison between our NM sample and national multiethnic datasets [64]. To construct the AIEHQ, we reviewed and selected pertinent questions on service experiences from the 2011 Access to Care component of the Medicare Current Beneficiary Survey [71], an annual in-person longitudinal panel survey. We also included relevant questions on health and health care from the 2012 National Health Interview Survey [17, 19, 72, 73], a cross-sectional in-person survey with a nationally representative household sample of the civilian non-institutionalized population; the Behavioral Risk Factor Surveillance System [2, 4, 6, 74], a telephone survey of adults; and the 2002 National Survey of American Families [75], based on a representative sample of the civilian, non-institutionalized population in 13 states. The AIEHQ features mostly closed-ended questions covering demographics; basic health status; healthcare access, utilization (place/ location and provider type), and barriers; health insurance (type of plan[s] and coverage of alternative medicine); culturally competent health care; healthcare satisfaction; health literacy; use of general/health-related technology; and anticipated health assistance. The AIEHQ takes approximately 30 min to complete.

##### *Qualitative data*

After the AIEHQ or during a separate meeting (to minimize respondent burden), participants will take part in a semi-structured qualitative interview that investigates the changing healthcare environment under the ACA and other reforms from the perspective of the AIEs, focusing specifically on contextual issues that bear upon their individual-level experiences and perceptions. Questions on the interview guide yield richly descriptive data on key issues affecting help-seeking and health care for AIEs; social, cultural, organizational, and system-related factors that influence access to and use of needed services; location of and general satisfaction with services; knowledge of and experience with the ACA, Medicare, Medicaid, and other insurance programs; enrollment into public insurance programs; the role of managed care (e.g., financing and service authorization mechanisms) in elder services; and overall health literacy concerns. Additionally, the interview guide will include the first step of the CM process (discussed in greater detail below), which asks participants to free-list or brainstorm items related to two focal questions with pertinent probes (i.e., “What factors make it easy or hard for American Indian elders to get good health care?” “What factors make it easy or hard for American Indian elders to get good health insurance?”). Each in-person interview will last approximately 45 min, be digitally recorded (depending on the language preferences of the participant, as described below), and occur in locations deemed private, accessible, and safe by participant and interviewer. Use of the guide increases the

comparability of responses and affords discretion to follow up on new or unexpected information.

An AIE Consultant will accompany the researchers in the field, consult on interview etiquette, help conduct interviews, and provide cultural and linguistic translations when necessary. After each interview, the researchers and AIE Consultant will “debrief” verbally about the encounter, i.e., highlights of what was learned, factors affecting data quality, and issues to explore in future interviews. The researchers will compile a written record of this debrief with review by the AIE Consultant.

We will conduct most interviews in English, with provisions for persons preferring to speak a Pueblo language. Due to the incredible linguistic diversity across Pueblos and the proximity of these communities to English-speaking populations, Pueblo residents are generally fluent in English [76]. Moreover, only tribal members appropriately have access to written and recorded texts in Pueblo languages [77], meaning that producing written interview scripts in Pueblo languages may violate local models of information control. Given these constraints, we will inform AIE participants that interviews (except for the CM component) can be conducted in the language of their choice. The AIE Consultants, who will be fluent in their respective AI languages, will implement the interview protocol when participants elect a language other than English. The researcher and the AIE Consultant will compile comprehensive field notes in English during and immediately after such interviews. With permission from participants, we will record the qualitative portions of all interviews undertaken in English. While in other research contexts it would be preferable to create audio or textual recordings of non-English interactions for back translation and quality assurance purposes (i.e., making certain that instrument implementation and accurate documentation of participant responses are uniform), doing so in this context would conflict with common cultural rules among the Pueblos regarding the collection and circulation of information concerning their heritage languages, and would likely result in feasibility and acceptability problems, and violate cultural codes. Cognitive pretesting of all instruments will ensure that their use does not create undue stress and burden for participants, are appropriate for the study population, and will yield desired information regarding insurance and healthcare issues.

#### *CM data*

The remaining CM exercises of pile-sorting and ranking will take place at a later date to reduce the possibility of participant fatigue, and last between 45 and 60 min [78–80]. The CM method is becoming increasingly prominent in community-driven, participatory research that seeks to determine locally relevant intervention strategies [81, 82]. It is useful when working with diverse stakeholders who may hold different perspectives on insurance and healthcare services. Two important CM goals are to further explore issues and themes identified in the qualitative interviews and to then generate a list of action items that are truly relevant to improving access and utilization among AIEs. The research team will identify approximately 80 unique statements from AIE answers to the focal questions contained in the semi-structured interview (i.e., “What factors make it easy or hard for American

Indian elders to get good health care?” “What factors make it easy or hard for American Indian elders to get good health insurance?”) and inscribe each statement on a card (e.g., “Having to travel long distances to get to the clinic,” “Having to wait too long for an appointment”). During the CM exercise, the participants will be asked to put similar

statements into piles. After the participant has created piles by grouping the statements, the researcher will ask the participant to describe the reasons for these choices and label each pile with a theme (e.g., “Transportation”). Finally, each participant will be asked to rank or rate each statement using a 1-to 10-point scale on three dimensions: 1) how much each statement affects American Indian elders; 2) how common each statement is among American Indian elders; and 3) how easy each statement would it be to change. This may appear a daunting task, but participants often see it as fun and engaging. Members of our research team have successfully deployed this technique with other vulnerable populations, including persons with serious mental illnesses.

### *Data analysis*

#### *Quantitative analysis*

We will use the quantitative data to summarize and compare characteristics of the AIE participants. Where possible, we will conduct descriptive comparisons that assess for differences between our study and AI and non-AI samples from other external studies that use the same questions. These results will help evaluate the extent to which the AIEs in our sample experience health access and utilization-related disparities. The anticipated quantitative analytical techniques include chi-square tests, t-tests, and ANOVAs. We will use multivariate regression strategies in exploratory analyses to identify characteristics associated with insurance and healthcare access and utilization outcomes among AIEs. An estimate of power is inappropriate given the qualitative sampling strategy guiding our overall sample selection.

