**Table 1. Overview of study phases, methods, and timeline**

	Phase 1: Convening AIE Advisory Board and Training AIE Consultants	Phase 2: Semi- structured Interviews and CM with AIEs (Aims 1 and 2)	Phase 3: Semi- structured Interviews and CM with Key Stakeholders (Aim 3)	Phase 4: Development, Implementation, and Evaluation of AIEONG (Aim 4)
Participant Category	
 
AIE leaders and Allies (<math>n = 20</math>; 8 Advisory Board members and 12 AIE Consultants)
 
	
 
AIEs (<math>n = 96-144</math>; 24-36 per region)
 
Sample stratified by age and gender to ensure adequate representation for men and women aged 55-64 and 65+
 
	
 
Outreach workers (<math>n = 12</math>)
 
Healthcare staff/providers (<math>n = 12</math>)
 
Public-sector administrators (<math>n = 12</math>)
 
Tribal leaders (<math>n = 12</math>)
 
	
 
AIE Navigators (<math>n = 16</math>; 8 in P1 and 8 in P2)
 
AIEs (<math>n = 48</math>; 12 per region)
 
Healthcare staff/providers (<math>n = 48</math>; 12 per region)
 

Sampling and Recruitment Strategy	
 
Reputational case selection (candidates identified based on recommendations from members of research team and local experts from NMICoA) [86]
 
	
 
Stratified purposive sample (candidates selected from AIE senior centers, healthcare settings, AIE Consultant referrals, and advertising to capture variations in the target population) [67]
 
	
 
Reputational case selection (candidates identified based on recommendations from local experts from NMICoA, healthcare support groups, and tribal programs) [86]
 
	
AIE Navigators:
 
 
Reputational case selection (candidates identified based on recommendations from local experts and interest in implementing AIEONG) [86]
 

				
AIEs and healthcare staff/providers
 
 
• List sampling (candidates selected from master lists that will be compiled from attendance records of individuals who participate in AIEONG-related activities or have contact with an AIE Navigator)
 

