## Research setting

As a culturally and geographically diverse state with the fourth-largest AI population in the U.S., New Mexico (NM) is an ideal setting in which to investigate the implications of federal-, state-, and/or tribal-led efforts to expand insurance options to AIEs under the ACA. The state also provides a unique opportunity to contextualize and compare AIE experiences in a range of healthcare venues located in both reservation and non-reservation settings. AIs comprise over 10.4% of 2,085,287 NM residents [60] and nearly 15% of NM's Medicaid population [61]. Prior to the first ACA enrollment period, close to 40% of all AIs in NM were uninsured. In 2016, 10.8% of AIs in NM were uninsured [60].

This research centers largely on the experiences of AIEs from NM's 19 Pueblos that are members of the NM Indian Title VI Coalition, Inc. (a confederation of programs that focus on AIEs, i.e., senior centers). The Pueblos are commonly divided into three broad geographical regions: North, South, and West, and include some tribes that have assumed total control over healthcare delivery from the IHS, some that rely on a combination of tribally-run 638 programs and IHS, and some that rely on the IHS at this time. The scope of options allows for richer comparisons of administrative and healthcare practices and policies affecting AIEs across regions. To broaden our sample and facilitate limited comparisons between rural and urban AIEs, we will also recruit non-reservation AIEs in the Albuquerque metropolitan area, home to an estimated 32,571 AIs from varied tribal backgrounds [62].

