#### *Phase 2: Semi-structured interviews and concept mapping (aims 1 and 2) with AIEs*

##### *Participants and recruitment*

To achieve Aims 1 and 2, we will use multiple strategies to recruit a total of 96 AIEs for completion of semi-structured interviews. We will identify potential participants by regularly visiting AI senior centers in the four regions (North, South, West, and Albuquerque), plus veterans organizations, community health fairs, and quarterly NMICoA meetings. We will use a qualitative sampling strategy designed to represent the range of views within a group (or region) to determine similarities and differences in knowledge, beliefs, and experiences related to the issues investigated [66, 67]. The domains of interest here are insurance coverage, help-seeking and healthcare experiences, and factors affecting AIE access and utilization. We will use purposive sampling to recruit candidates able to discuss the elements of these domains. Unlike probability sampling procedures, in purposive sampling there is no way to precisely estimate how many of each type of participant might be required for a study. However, qualitative researchers generally agree that in-depth interviewing requires between 12 and 26 persons within a designated group [67– 69]. We have calculated the interview sample sizes with AIEs accordingly; each is large enough to examine a range of experiences related to the topics at hand. If, during the process of obtaining informed consent from AIE participants, the researcher or AIE Consultant feels that a potential participant may not be able to understand or complete study procedures, they will

administer the MINI-COG [70] to test for cognitive impairment. Participants deemed positive for cognitive impairment will not be eligible to participate.

After completion of the semi-structured interviews, we will use the same strategies to recruit 48 AIEs who can read in English to participate in the remaining CM exercises (described below). These may, but will not necessarily, include individuals who participated in semi-structured interviews.

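### The named tests treat elders as independent; if elders in the same community answer alike, regional comparisons will look more precise than they are

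*Combined protocol and SAP*

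**What the plan says.** **Tests.** Under Phase 2, Quantitative analysis: "The anticipated quantitative analytical techniques include chi-square tests, t-tests, and ANOVAs". The same paragraph adds exploratory regressions of unstated form and declines a power estimate because the sampling is qualitative. CM analysis lists region among the characteristics to be examined empirically and then names t-tests on the cluster rankings. Phase 3 follows the Phase 2 procedures.

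**Recruitment.** The Phase 2 text plans to "recruit a total of 96 AIEs for completion of semi-structured interviews"; Table 1 gives "24-36 per region". On sources: "We will identify potential participants by regularly visiting AI senior centers in the four regions (North, South, West, and Albuquerque), plus veterans organizations". Health fairs and council meetings are also named, and Table 1 adds healthcare settings, referrals and advertising.

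**Structure.** Research setting centers the study on "NM's 19 Pueblos that are members of the NM Indian Title VI Coalition, Inc", grouped into three regions. Some tribes run all their own care; there are also "some that rely on a combination of tribally-run 638 programs and IHS, and some that rely on the IHS at this time". This variety is said to allow "richer comparisons of administrative and healthcare practices and policies affecting AIEs across regions". Albuquerque forms a fourth, non-reservation region.

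**Not stated.** There is no ICC, number of sites, elders per site, site identifier, robust variance or random effect.

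**The concern.** Elders of one Pueblo may use the same clinics, the same senior center and the same delivery arrangement. Their answers on access, use, barriers and satisfaction may therefore be more alike than answers from different communities. Because Pueblos sit inside regions, a contrast among North, South and West is a contrast among a limited number of communities. A test that counts elders rather than communities then understates the uncertainty.

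At stake is whether chance differences between a few communities are read as regional differences. The plan uses quantitative results to direct closer qualitative analysis, and Phase 2 and 3 findings feed the navigation guide. If site is not recorded, the correction may not be possible later.

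**Working it through.** **1. The plan's own figure.** 4 regions × 24 = 96 and 4 × 36 = 144, which reproduces Table 1. The Phase 2 text gives only 96. No alpha, ICC or precision figure is stated, so everything below is illustrative, with a two-sided alpha of 0.05 assumed.

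**2. Design effect for a contrast between two Pueblo regions.** With m elders per community:

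- DEFF = 1 + (m − 1) × ICC
- the interval should be wider by a factor of √DEFF
- actual error of a nominal 5% test ≈ 2 × [1 − Φ(1.96/√DEFF)]

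If all 19 Pueblos are sampled, m = 3 × 24/19 = 3.8. If three sites per region are sampled, m = 24/3 = 8.

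| m | ICC | DEFF | Width factor | Actual error |
|---|---|---|---|---|
| 3.8 | 0.01 | 1.03 | 1.01 | 5.3% |
| 3.8 | 0.10 | 1.28 | 1.13 | 8.3% |
| 8 | 0.01 | 1 + 7 × 0.01 = 1.07 | 1.03 | 5.8% |
| 8 | 0.10 | 1 + 7 × 0.10 = 1.70 | 1.30 | 13.3% |

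At 36 elders per region with all 19 Pueblos, m = 108/19 = 5.7. At ICC 0.10, DEFF is 1.47 and the width factor 1.21, so a larger sample from the same communities makes the problem worse.

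**3. Four-region ANOVA by simulation under a true null.** The outcome is normal with total variance 1, a community effect of variance ICC and an elder effect of variance 1 − ICC. There are 24 elders per region. Albuquerque elders are independent. The 19 Pueblos are split 6, 6 and 7 (an assumed split), or three sites of 8 elders are drawn per Pueblo region. The entries are the share of null datasets rejected at 5%; repeated runs agree to within about one percentage point.

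| ICC (assumed) | 6–7 Pueblos per region | 3 sites per region |
|---|---|---|
| 0.01 | 5% | 6% |
| 0.05 | 7% | 10–11% |
| 0.10 | 9–10% | 16–17% |
| 0.20 | 14–15% | 29% |

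**4. Delivery system.** The direction depends on the layout. With 96 elders, all four regions clustered and ICC 0.10, an ordinary t-test gives the following:

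- Setting constant within a site: rejects 8.5% (sites of 4), 11.2% (sites of 6) and 17.9% (sites of 12).
- Setting split evenly within each site: rejects about 4%, which is slightly conservative.

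**5. Scope.** These figures are for the 96 interviewed elders. The concept-mapping subset has 48 elders and no stated regional split. The same mechanism applies there, but the percentages do not carry over.

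**The case against.** The strongest reply is that no primary conclusion depends on these tests. The study calls itself mainly descriptive, its qualitative part dominates, and the sample is purposive. Nominal error rates from such a sample have no design-based meaning even after a cluster correction. The tests are only anticipated, and the regression form is open, so a mixed model is not ruled out. All of this stands and lowers the priority. It does not make the independence assumption harmless where tests are reported.

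Second, the Quantitative analysis paragraph does not name region or care setting. That is correct. The explicit link between region and a named test is in CM analysis; the wish to compare across regions is in Research setting and concerns practices and policies.

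Third, the nesting is incomplete. Albuquerque elders come from varied tribal backgrounds, and several recruitment routes are not senior centers. This also stands, and is why Albuquerque is treated as unclustered above. The effect shrinks but does not vanish.

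A reader might go further in three ways that the documents do not support:

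- *That the plan itself says access, use and satisfaction are shared within a Pueblo.* It says only that delivery arrangements differ by tribe. Positive correlation is an inference from that.
- *That every care-setting comparison is too liberal.* The questionnaire records each elder's place of care, provider type and plan, so setting can vary within a community. There the ordinary test can be slightly conservative.
- *That error reaches about 37%.* That needs ICC 0.20, three sites per region and clustering in Albuquerque as well, all assumed.

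**Conclusion.** The point holds conditionally. If within-community correlation is positive, ordinary tests of regional differences reject too often and their intervals are too narrow. The same applies to delivery-system comparisons where the system is constant within a community. It does not extend to care settings that vary within a community.

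The size cannot be fixed from the documents. Under the stated assumptions it runs from negligible (about 5–6% at ICC 0.01) to substantial (29% at ICC 0.20 with three sites per region). With most Pueblos sampled and ICC no higher than 0.10, it stays at or below about 10%. A reader might take it as established that the error bars are too narrow, but without an ICC or site count that is not shown. Equally, the plan gives no basis for saying that the effect is small. Given the descriptive aim and purposive sample, this is a worthwhile improvement rather than an essential one.

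**What to change.** 1. Record a coded, unnamed identifier of community or recruitment site for each elder.
2. For comparisons by region, by reservation versus non-reservation residence, and by delivery system defined at community level, use a mixed model with a random community intercept, or cluster-robust errors with a small-sample correction. Include the concept-mapping ratings and the exploratory regressions.
3. State how Albuquerque elders enter: grouped by recruitment site, or unclustered.
4. If this is not wanted, report these comparisons descriptively, without p-values.

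The cost is one coded variable, a short addition to the analysis text and a decision on Albuquerque. The downside is somewhat wider intervals for between-community contrasts: by a factor of 1.13 at ICC 0.10 with all 19 Pueblos sampled, or 1.30 with three sites per region, at 24 elders per region.

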#### *Qualitative analysis*

We will employ an iterative process to analyze textual qualitative data. First, we will assign codes to segments of text ranging from a phrase to several paragraphs based a priori on topics and questions in the interview guides. We will then engage in open coding to identify and define new codes related to themes and issues not previously considered, followed by focused coding to determine which of these themes/issues recur and which represent unusual concerns to participants [83]. By constantly comparing and contrasting codes with one another, we will group codes with similar content or meaning into broader themes linked to retrievable segments of text [83, 84]. As part of the process, we will triangulate interview findings across several dimensions

(e.g., gender, region, age group, insurance/coverage type, etc.). Here, we will create a matrix detailing specific themes pertinent to key study issues outlined in our specific aims and the SEM (e.g., enrollment implicated at the individual, organizational/community, and policy levels), and supporting data from participants. We will then engage in a side-by-side comparison of various perspectives from AIEs across regions or other key dimensions to identify points of convergence and divergence in statements related to the specific themes/issues under consideration. In this staged approach, researchers will code sets of notes and transcripts, create detailed memos that describe and link codes to each theme/issue, and then pass on this work to the co-investigators for review. Discrepancies in coding and analysis will be identified during this review process and resolved during regular team meetings. Products of this process will include a summary report of key themes/issues that cross cut and are particular to specific types of participants.

